10.3.1 Primary endpoint

The primary objective of the trial is to investigate the safety of selected t_{\max} settings in the insulin-only configuration of the iLet™ bionic pancreas using fast-acting insulin aspart in adults with T1DM in a short-term, outpatient clinical trial. The primary endpoint to address this objective is:

- Time in low interstitial glucose (defined as below 54 mg/dL [3 mmol/L]) from initiation of treatment (day 1) to end of treatment (day 7) (percentage)

This will be derived as the percentage of available interstitial glucose values below 54 mg/dL (3 mmol/L)

The assessment of the primary endpoint will be based on descriptive summaries presenting mean, median, minimum and maximum values by cohort and treatment.

Supplementary analysis for the primary analysis

The default t_{\max} setting (t_{65}) will be compared to each of the non-default t_{\max} settings (t_{50} , t_{40} and t_{30}) separately by cohort for time spent in low interstitial glucose (defined as below 54 mg/dL [3mmol/L]) using a linear mixed effect model with treatment and period as fixed effects and subject as random effect. This is done to investigate the treatment differences from a within-subject perspective.

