3.3 Benefit-risk assessment

The current trial will evaluate different settings of the algorithm in the iLet[™] using fast-acting insulin aspart. The currently available data demonstrate that treatment with fast-acting insulin aspart results in an increased early absorption of fast-acting insulin aspart compared to NovoLog[®], thereby providing a faster action. It is expected that this clinical trial will yield increased knowledge about using fast-acting insulin aspart in an automated closed-loop system to control the glucose level. The individual subject may not benefit from study participation.

For the individual subject, the anticipated risks include hypoglycaemia, hyperglycaemia, infusion site reactions, CGM related inconveniences, systemic allergic reactions and antibody development.

As in any other clinical trials with T1DM patients, hypoglycaemia and hyperglycaemia are a risk in subjects in this clinical trial as well. Hypoglycaemia could occur if the system delivers an inappropriate amount of insulin given the subject's underlying glycaemic state. This could occur if, for example, a sensor is functioning poorly and significantly over-reads glucose values. Over-delivery may be minimized if the sensor's trend data remains accurate despite inaccurate level values, or by the safety constraints of the closed loop system. However, there is a risk of having a low blood sugar (hypoglycaemia) that may exceed the risk present as part of normal daily living. Hypoglycaemia could also occur if the t_{max} setting of the control algorithm is set to a value that is too low relative to the actual t_{max} setting of the insulin being administered to a particular research subject, leading to insulin stacking. Symptoms of hypoglycaemia can include sweating, jitteriness, and not feeling well. Hyperglycaemia and ketonaemia could occur if insulin delivery is attenuated or suspended for an extended period or if the pump or infusion set is not working properly. A sensor which was functioning poorly and significantly under-reading glucose values could lead to inappropriate reduction of insulin delivery.

There is a potential risk of hypoglycaemia, hyperglycaemia and potentially diabetic ketoacidosis in case of technical problems with the iLet[™].

Remote monitoring is implemented in this trial and should minimize these risks of hypoglycaemia and hyperglycaemia to the extent possible, see section [9.16](#).

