8.1.1 Escalation stopping criteria

After all subjects have completed Visit 4 in a given cohort, the PI will evaluate if any of the following have occurred in individual subjects:

- Time in low interstitial glucose (defined as below 54 mg/dL (3.0 mmol/L)) is higher than 2% of the total time from initiation of treatment (day 1) to end of treatment (day 7) on the same t_{\max} , or,
- One or more episodes of treatment emergent severe hypoglycaemia (see [Appendix 7](#) for definition) have occurred from initiation of treatment (day 1) to end of treatment (day 7) on the same t_{\max}

For each subject and for each treatment period, the time in low interstitial glucose (percentage) and number of treatment emergent severe hypoglycaemia episodes as per the above evaluation must be recorded in the CRF.

Escalation decision

If any of the above specified events occur in two or more subjects on the same t_{\max} setting within a cohort, continuation to the next cohort with a lower t_{\max} setting will not occur. Concretely, continuation to the next cohort with a lower t_{\max} setting will not occur in the following scenarios:

- Time in low interstitial glucose (defined as below 54 mg/dL (3.0 mmol/L)) is higher than 2% of the total time from initiation of treatment (day 1) to end of treatment (day 7) on the same t_{\max} in two or more subjects,
- One or more episodes of treatment emergent severe hypoglycaemia (see [Appendix 7](#) for definition) have occurred from initiation of treatment (day 1) to end of treatment (day 7) on the same t_{\max} in each of two or more subjects,
- Time in low interstitial glucose (defined as below 54 mg/dL (3.0 mmol/L)) higher than 2% of the total time from initiation of treatment (day 1) to end of treatment (day 7) on the same t_{\max} in one or more subjects and one or more episodes of treatment emergent severe hypoglycaemia (see [Appendix 7](#) for definition) have occurred from initiation of treatment (day 1) to end of treatment (day 7) on the same t_{\max} in one or more subjects.

The escalation decision at the end of the cohort must be documented by the PI. If the escalation decision is to not open the next cohort, then the subjects who are in screening will be registered as withdrawn and an end-of-trial form must be completed.

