10.3 Statistical analyses

If necessary, a statistical analysis plan (SAP) may be written in addition to the protocol, including a more technical and detailed elaboration of the statistical analyses. The SAP will be finalised before database lock.

Endpoints and derivations based on the interstitial glucose profiles will be summarised and analysed using the FAS, unless otherwise stated. The other endpoints will be summarised using the safety analysis set and analysed using the FAS.

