10.3.4.3 Escalation decision

For each of the two escalation stopping criteria defined in section [8.1.1](#) , the number and percentage of subjects fulfilling the criteria will be presented separately by cohort and treatment.

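### Does the supplementary mixed model for time below 54 mg/dL need a stated interval, degrees-of-freedom method and paired listing?

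*Combined protocol and SAP*

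**What the plan says.** The primary endpoint is the percentage of available interstitial glucose values below 54 mg/dL over each 7-day period. Section 10.3.1 makes its assessment descriptive: "The assessment of the primary endpoint will be based on descriptive summaries presenting mean, median, minimum and maximum values by cohort and treatment". A supplementary comparison of default and lower setting follows, cohort by cohort, "using a linear mixed effect model with treatment and period as fixed effects and subject as random effect". The stated purpose is: "This is done to investigate the treatment differences from a within-subject perspective".

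Neither this section nor any other gives a transformation, interval level, significance level or degrees-of-freedom method. None of the four amendments alters section 10. Further technical detail is left to a separate document that is optional (section 10.3): "If necessary, a statistical analysis plan (SAP) may be written in addition to the protocol".

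Two other places bear on the point. Section 8.1.1 requires the percentage to be entered in the CRF by subject and by treatment period, and its escalation rule counts individuals: "If any of the above specified events occur in two or more subjects on the same" t_max setting, the next cohort does not open. Section 10.3.4.3 reports the two criteria so that "the number and percentage of subjects fulfilling the criteria will be presented separately by cohort and treatment".

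**The concern.** The benefit-risk text (section 3.3) describes a hazard that belongs to individuals: a t_max set too low relative to the "setting of the insulin being administered to a particular research subject, leading to insulin stacking". Section 5.4 justifies the cross-over by its within-subject comparison. Yet the only planned output that uses the pairing is an average over eight people.

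If one or two subjects rose sharply and the rest did not move, that average could come with an interval spanning zero and be read as no within-subject change. The tables by treatment would show a high value on the lower setting, but might not show whether the same subject was equally high on the default. With no interval or degrees-of-freedom method fixed, the model result could also be reported in more than one way. What is at stake is the reading of the within-subject result, not a decision in the trial.

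**Working it through.** **Inputs.** Eight subjects per cohort (section 10.1). Randomisation 1:1 to two sequences (section 5.1), taken as 4 + 4, all complete. The model has treatment, period and subject (section 10.3.1). The sample size rests on no formula, so there is no power or precision figure to reproduce. A two-sided 5% t test is an assumption, since the documents state none.

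**Degrees of freedom.** 16 observations − 8 subjects − 2 (treatment and period) = 6. The critical value is 2.447.

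**Formula.** For complete data, work with each subject's difference (lower setting minus default). The estimate is the mean of the two sequence-specific mean differences. With s² the pooled within-sequence variance of the differences, SE = √(s²/8).

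**One subject rises by d, the others unchanged.**
- Estimate = (d/4 + 0)/2 = d/8.
- Within-sequence sum of squares = d² − d²/4 = 0.75d², so s² = 0.75d²/6 = 0.125d².
- SE = √(0.125d²/8) = d/8.
- t = 1.00, p = 0.36, for every d.

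**Two subjects rise, one in each sequence.** t = (d₁ + d₂)/√(d₁² + d₂²), which is at most 1.41 (equal rises, p = 0.21).

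**Two subjects rise, same sequence.** For equal rises the sum of squares is 2d² − d² = d², so s² = d²/6 and SE = √(d²/48) = 0.144d. The estimate is d/4, giving t = 1.73 (p = 0.13). Unequal rises give less.

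A larger rise inflates the residual variance as fast as it moves the estimate. For a 20-point rise in one subject the estimate is 2.5, with 95% interval 2.5 ± 2.447 × 2.5 = −3.6 to 8.6. For two such rises in one sequence it is 5.0 (−2.1 to 12.1). Subjects who do not change have zero difference on any scale, so a square-root or log transformation does not escape these limits.

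**How firm the limits are.** They take the subject variance as unconstrained. If a REML fit sets it to zero, two risers in opposite sequences give about 1.47 on 13 degrees of freedom (p = 0.17), still short of significance. With 3 + 4 completers and both risers in the smaller group, t = 2.39 on 5 degrees of freedom (p = 0.06). With 3 + 3 and both in one sequence, t is at most 2.0 on 4 (p = 0.12). The limit fails only in a corner case, such as two completers left in one sequence, both of them risers.

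**With noise** (simulated, 100,000 trials per setting). Under normal noise and rises from 0 to 50 SDs of the difference, the chance of a significant rise peaks at about 4% for one riser. For two it peaks at 7–8% (opposite sequences) or 11–12% (same sequence). Skewed gamma backgrounds with mean 0.3–1.0% give at most about 11% on the raw scale and 13% on the log scale. With a normal reference or a one-sided 5% test the peaks are about 9%, 16% and 26%. By contrast, a shift of one SD of the difference in all eight subjects is significant in 66% of trials. The model therefore does its own job, which is to estimate an average shift.

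**What the other planned outputs catch.**
- The maximum by treatment shows any large value. The subject with the highest value on the lower setting had, on the default, no more than the default maximum. That subject's rise is therefore at least the lower-setting maximum minus the default maximum. The tables leave the question open only when both maxima are high.
- Two subjects above 2% on one setting prevent the next cohort from opening, whatever the model shows.
- The paired values are in the CRF, so listing them needs no new data.

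**The case for a change.** The case for a change is reasonable. The plan announces a within-subject perspective, the hazard is individual, and the one within-subject output is a mean that can hardly reveal it. Adverse events are to be listed (section 10.3.2.1), while the primary glucose endpoint has no planned listing. The chance of a significant result depends on reference and sidedness, which are not fixed. A sentence naming the interval and degrees of freedom, with an eight-row listing per cohort, would cost almost nothing.

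The textual gap stands, and so does the arithmetic. The consequence does not. The misreading that is feared needs an interval or test that the plan does not specify, and writing one in would not make the mean difference any better at showing an individual rise. The scale is not truly open, because the endpoint is defined as a percentage and no transformation is mentioned. With complete data, 6 degrees of freedom follow from the design itself, unless the subject variance is estimated at zero. The point estimate still moves, by d/8 for one riser and d/4 for two equal ones. A paired listing would be a helpful display, but a single 7-day period per setting makes each pair noisy, and a rise may reflect period or chance. It would have to be labelled descriptive, which is already the status of the primary assessment.

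**Conclusion.** No change to the plan is needed. Section 10.3.1 leaves out an interval level and a degrees-of-freedom method, and no paired listing or plot is specified. These are details that an analyst fills with ordinary defaults from data already collected. The mean difference is a weak display of an effect confined to one or two of eight subjects: t of about 1.0, or at most about 1.4–1.7, against 2.447. That is true of any mean over eight, on any scale, so tighter model wording would not cure it. The plan does not depend on the model for that purpose, because it has the maximum by treatment and the counts of subjects over 2%.

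The t values assume 4 + 4 complete subjects, no change in the others and a two-sided 5% t reference. Other references raise the chance of a significant result to about 26% at most in the settings simulated. No decision in the trial rests on that result. A team that writes the optional SAP may add the interval and a per-subject listing for the reader's convenience.

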3.2 Background

3.2.1 Therapeutic area and the iLet™

The bionic pancreas consists of a combination of an insulin pump, a continuous glucose monitoring system, and mathematical dosing algorithms developed at Boston University and the Massachusetts General Hospital. Based on the individual subject's continuous glucose measurement (CGM) readings, the device autonomously delivers insulin and/or glucagon and manages the patients' blood sugar levels. The mathematical dosing algorithm determines dosing requirements in steps every five minutes adapting continually to each individual's ever-changing insulin needs. The adaptive meal-announcement algorithm eliminates the need for the user to set or know their carbohydrate-to-insulin ratios, as it makes automatic adjustments based on dosing history for similar past meal announcements, and customizes its doses to the individual and time of day to meet a target of 75% of the insulin needs for that size and mealtime. Previous trials with the bionic pancreas have shown an improved mean glucose and reduced time in hypoglycaemia and hyperglycaemia compared to the current standard of treatment^{2,3}. The bionic pancreas device, hereafter referred as the iLet™,

developed by Beta Bionics, integrates all the components of the Boston University–Massachusetts General Hospital bionic pancreas into a single hand-held medical device.

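### Should the supplementary within-subject comparison of time below 54 mg/dL also be prespecified on a log scale?

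*Combined protocol and SAP*

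**What the plan says.** Section 10.3.1 defines the endpoint on the percentage scale: "This will be derived as the percentage of available interstitial glucose values below 54 mg/dL". Its assessment is descriptive: "The assessment of the primary endpoint will be based on descriptive summaries presenting mean, median, minimum and maximum values by cohort and treatment".

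A supplementary analysis then compares t65 with t50, t40 and t30 "separately by cohort for time spent in low interstitial glucose", "using a linear mixed effect model with treatment and period as fixed effects and subject as random effect". Its stated purpose is limited: "This is done to investigate the treatment differences from a within-subject perspective". No transformation and no rule for zeros is given, in the protocol or in Amendments 1 to 4.

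Section 10.1 plans 8 subjects per cohort without a formal sample size calculation. Section 10.3 leaves technical detail to an optional SAP: "The SAP will be finalised before database lock". Section 8.1.1 bases escalation on the number of individual subjects above 2% of time below 54 mg/dL or with severe hypoglycaemia, and Section 10.3.4.3 reports those counts by cohort and treatment.

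**The concern.** Time below 54 mg/dL is bounded at zero, is likely to sit close to that bound, and may be exactly zero in some subject-periods. A normal-error model on such values in 8 subjects leaves 6 residual degrees of freedom, too few for averaging to remove much skew. If a lower t_max raises exposure in proportion to a subject's level, or only in some subjects, the within-subject differences are skewed to the right. Mean and standard error then move together, and a t interval tends to fall short of the true increase.

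For a safety endpoint that is the unwelcome direction. This is also the plan's only within-subject comparison of the primary endpoint, and a second analysis on log(% + 0.05) would cost very little. At stake is how the t65 contrast in each cohort is read.

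**Working it through.** **Inputs.** From the documents: 8 subjects per cohort, 1:1 to two sequences, two 7-day periods, and the model above. The documents give no SD, zero rate, t65 level, alpha or interval level. Assumed: two-sided 5% tests, 95% t intervals, 4:4 allocation and the distributions named below. Simulated rates are from 40,000 cross-over cohorts per setting.

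**1. What depends on the model.** The primary assessment uses mean, median, minimum and maximum. The escalation rule uses subject counts. Neither uses the model.

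**2. Bias.** With complete data, let d be a subject's non-default minus default value. The model's treatment estimate is ½ × (mean d in one sequence + mean d in the other). The period effect cancels, and normality is not needed for the expectation, so skew does not bias the mean difference. Residual df = 16 observations − 8 subjects − 1 treatment − 1 period = 6.

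**3. No effect.** Raw-scale rejection at nominal 5% is 1.5% to 3.0% with lognormal data and 3.2% to 4.3% with episode-type data. The raw analysis is conservative. With a uniform shift of +0.6 points, the interval lies wholly below the truth in 0.8% to 1.5% of trials.

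**4. A true doubling of the mean.** The nominal rate for an interval wholly below the truth is 2.5%.

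| Assumed data | Raw interval wholly below true increase | Power, raw | Power, log(% + 0.05) |
|---|---|---|---|
| Mild skew (log-SDs 0.4 to 0.5, 5% zeros), two settings | 4.9%, 6.7% | 54.3%, 37.1% | 50.7%, 41.7% |
| Episode-type (11% to 40% zeros), four settings | 5.6% to 7.6% | 42.4%, 48.2%, 24.7%, 17.5% | 40.1%, 46.4%, 27.3%, 22.3% |
| Lognormal, 10% zeros, (between, within) log-SD (0.7, 0.7), (1.0, 0.8), (1.2, 1.0) | 9.5%, 14.1%, 18.8% | 14.0%, 8.0%, 4.1% | 19.7%, 17.6%, 13.7% |
| A quarter of subjects rise 5-fold (mean 0.75 × 1 + 0.25 × 5 = 2) | 17.5% to 24.2% | not tabulated | not tabulated |

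The upper tail misses less often than nominal, so two-sided coverage suffers less than the one tail suggests: 94.1% and 93.0% with mild skew, and about 90%, 85% and 80% in the lognormal cases (assumed t65 mean 0.6%).

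**5. What a log version would deliver.**

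- *Zeros.* A cohort has 16 subject-periods, so P(at least one zero) = 1 − (1 − p)^16: 28%, 56%, 81% and 97% for p = 2%, 5%, 10% and 20%. An offset is therefore usually needed.
- *Offset.* A value of 0.05 is one reading in 7 × 288 = 2,016 (0.0496%). This borrows the algorithm's step, which "determines dosing requirements in steps every five minutes", as the CGM interval, which the protocol does not state. The flowchart lets a period be one day short: 6 × 288 = 1,728 readings, or 0.058% each.
- *Shrinkage.* For a true ratio of 2 in the three lognormal cases, the median estimate is 1.78, 1.69 and 1.56 at offset 0.05, and 1.71, 1.59 and 1.45 at 0.1.
- *Subset response.* Even without zeros or an offset, the log model targets a geometric mean ratio, 5^0.25 = 1.50, although the arithmetic mean doubles. With zeros and the 0.05 offset the median is 1.3 to 1.4, and 8% to 13% of log intervals lie wholly below 2.
- *Sensitivity.* In an invented 8-subject cohort with one zero on each treatment, p was 0.149, 0.070, 0.026 and 0.005 at offsets 0.025, 0.05, 0.1 and 0.5. The raw analysis gave 0.025.

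**6. Adding an exact test.** With 4:4 allocation there are C(8,4) = 70 allocations, so the smallest two-sided p-values are 2/70 = 0.029 and 4/70 = 0.057. Its power is 16%, 12% and 9% on the raw scale in the lognormal cases, and 15%, 12% and 9% on the log scale. It would protect validity in an analysis that is already conservative under no effect.

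**The case for a change.** The best case for a log version is that the one-sided miss is real and of the wrong sign for safety. Section 3.3 describes a plausible subset mechanism, in which the setting is too low for a particular subject's insulin absorption and doses stack. Where zeros are rare, the log scale can gain a good deal: with no added zeros, between-subject log-SD 0.8 and within-subject log-SD 0.5, power for a doubling is about 34% raw against 62% to 64% with a half-reading offset. Fixing the scale and offset before database lock would also prevent a choice made after seeing the data.

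Much of this stands. The raw interval can undercover, the plan does not name its scale or its handling of zeros, and a log analysis could be added cheaply. But the power gain depends on rare zeros. In the same set of calculations it falls to 22% raw against 24% to 34% at 10% zeros, and to 12% to 13% against 10% to 17% at 25% zeros. The subset mechanism is the case in which the ratio understates the mean increase most. The log interval misses its own target in only 1.1% to 3.0% of trials, but that target has already been moved by zeros and the offset, so it is not comparable with the raw interval's miss of the true mean increase. The raw interval itself would be reported unchanged.

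**Conclusion.** The concern does not hold as a fault in the plan. The model answers its stated descriptive question, the difference in mean time below 54 mg/dL within subjects, on the same scale as the 2% limit in Section 8.1.1. It does so without bias when data are complete. Neither the primary assessment nor the escalation decision depends on it.

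Its limitation is an interval that may lie below a true doubling in roughly 5% to 24% of trials instead of 2.5%. That range is set entirely by assumed distributions, and both the 95% level and the t interval are assumptions too. A log(% + c) model replaces this limitation with others: a different estimand, dependence on c, and attenuation towards 1. With mildly skewed or episode-type data it changes power by only −4 to +5 points. With 8 subjects neither scale reliably detects a doubling. Statisticians could reasonably choose either, and the optional SAP can still state the scale.
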